## List of Abbreviations

Abbreviation	Definition
ACE2	Angiotensin-converting enzyme 2
ADE	Antibody-dependent enhancement
ADR	Adverse drug reaction
AE	Adverse event
ALT	Alanine aminotransferase
AMS	Aseptic meningitis syndrome
ANTHRASIL®	Anthrax immune globulin intravenous (human)
ARDS	Acute respiratory distress syndrome
AST	Aspartate aminotransferase
AUC	Area under the concentration-time curve
BMI	Body mass index
BUN	Blood urea nitrogen
CBC	Complete blood count
CCP	COVID-19 convalescent plasma
CFR	Code of Federal Regulations
C max	Maximum serum concentration
CNJ-016®	Vaccinia immune globulin intravenous (human)
COVID-19	Coronavirus disease 2019
COVID-HIGIV	Anti-SARS-CoV-2 Immunoglobulin Intravenous (Human)
CRF	Case report form
CV	Coefficient of variation
DMP	Data management plan
EC	Ethics committee
ECMO	Extracorporeal membrane oxygenation
eCRF	Electronic case report form
EDC	Electronic data capture
FDA	Food and Drug Administration in US
GCP	Good clinical practices

## Clinical Study Protocol EBS-CVH-003

Version 4.0, 21 Apr 2021

Abbreviation	Definition
HBV	Hepatitis B virus
HCV	Hepatitis C virus
HepaGam B®	Hepatitis B immune globulin (human)
HIV	Human immunodeficiency virus
ICH	International Council for Harmonisation of Technical Requirements for Pharmaceuticals for Human Use
ICU	Intensive care unit
IEC	Independent ethics committee
IgA	Immunoglobulin A
IgG	Immunoglobulin G (gamma globulin)
IgM	Immunoglobulin M
IGIV	Immunoglobulin intravenous
IL-1	Interleukin-1
IL-6	Interleukin-6
IP	Investigational product
IPD	Important protocol deviation
IRB	Institutional review board
IV	Intravenous route of administration
LDH	Lactate dehydrogenase
LLOQ	Lower limit of quantitation
LOD	Limit of detection
LOQ	Limit of quantitation
mAb	Monoclonal antibody
MedDRA	Medical Dictionary for Regulatory Activities
MM	Medical monitor
NP-028	Anti-SARS-CoV-2 Immunoglobulin Intravenous (Human)
OHRP	Office for Human Research Protection
PE	Physical exam
PEP	Post-exposure prophylaxis
PI	Principal investigator
PK	Pharmacokinetics

## Clinical Study Protocol EBS-CVH-003

Version 4.0, 21 Apr 2021

Abbreviation	Definition
ppm	Parts per million
PS80	Polysorbate 80
PSO	Post symptom onset
PT	Pregnancy test
PT/PTT	Prothrombin time/partial thromboplastin time
REB	Research ethics board
RNA	Ribonucleic acid
RTSM	Randomization and trial supply management
RT-qPCR	Reverse transcriptase quantitative polymerase chain reaction
RT-PCR	Reverse transcriptase polymerase chain reaction
SAE	Serious adverse event
SAP	Statistical analysis plan
SAR	Serious adverse drug reaction
SARS-CoV-2	Severe acute respiratory syndrome coronavirus 2
SD	Standard deviation
SMC	Study monitoring committee
SOC	System organ class
SUSAR	Suspected unexpected serious adverse drug reactions
T ½	Apparent first order terminal elimination half-life
T max	Time at which C max occurs
TnBP	Tri-n-butyl phosphate
TNF-α	Tumor necrosis factor alpha
TRALI	Transfusion-related acute lung injury
TX-100	Triton X-100 (octyl phenylpolyethylene glycol ether)
UPT	Urine pregnancy test
US	United States of America
VARIZIG®	Varicella zoster immune globulin intravenous (human)
VIGIV	Vaccinia immune globulin intravenous (human)
WinRho® SDF	Rh o (D) immune globulin intravenous (human)
WHO	World Health Organization

## 1 INTRODUCTION

### 1.1 Background Information

#### 1.1.1 Severe Acute Respiratory Syndrome Coronavirus 2 (SARS-CoV-2) and Coronavirus Disease 2019 (COVID-19)

The COVID-19 pandemic caused by SARS-CoV-2 has resulted in significant worldwide increase in hospitalizations for pneumonia with multiorgan failure (1). In December 2019, a cluster of patients with pneumonia of unknown cause in Wuhan, China was reported and by January 2020 the causative agent of the illness was identified; initially termed novel coronavirus 2019 (2019-nCoV) and later renamed to SARS-CoV-2 (2). Due to the spread of SARS-CoV-2 resulting in sudden increase in COVID-19 cases throughout the world, a pandemic was declared by World Health Organization (WHO) in March 2020. By early September 2020, >26 million COVID-19 cases and >864,000 COVID-19 attributed deaths have been reported to the WHO.

SARS-CoV-2 transmission typically occurs via respiratory droplets from close face-to-face contact (within six feet/two meters) and, to a lesser degree, via contaminated surfaces (3). Aerosol spread (airborne transmission) may occur (4), but the role of airborne transmission in humans remains unclear (5). It is estimated that up to 62% of SARS-CoV-2 transmission may occur via pre-symptomatic carriers (3).

SARS-CoV-2 utilizes its envelope homotrimeric Spike (S) glycoprotein to interact with a cellular receptor on human cells termed angiotensin-converting enzyme 2 (ACE2). Binding with ACE2 triggers a cell membrane fusion cascade leading to viral cellular entry (6), (7). Cell types within tissues of nasopharynx, lung, heart, esophagus, kidney, bladder and ileum (i.e., type II alveolar cells, myocardial cells, proximal tubule cells of the kidney, ileum and esophagus epithelial cells, and bladder urothelial cells) express ACE2, which suggests tissue targets for SARS-CoV-2 infection (8), (9).

SARS-CoV-2 viremia starts in the upper respiratory tract, and typically peaks around time of symptom onset (4-5 days post-infection); however, viral shedding starts 2-3 days prior to symptom onset (10). Pharyngeal viral shedding is high within the first week post-infection at a time when symptoms are typically mild (11). Although SARS-CoV-2 RNA can be detected in throat swabs for up to six weeks after the onset of symptoms, viral cultures are generally SARS-CoV-2 negative 8 days after symptom onset (10), (11), (12).

Humoral immune response is induced during SARS-CoV-2 infection; IgM and IgA antibodies are typically detectable 5 days (range: 3-6 days) post symptom onset (PSO), while IgG antibodies are detectable 14 days (range: 5-18 days) PSO (13), (14). The IgM response starts to decline 25-30 days PSO, while IgA and IgG responses remain stable 40 days (15) and 3 months PSO (16), respectively. Neutralizing SARS-CoV-2 antibodies are detectable 10-15 days post symptom onset (13) and can persist up to 3 months (16). T-cell responses against SARS-CoV-2 Spike protein have been characterised and correlated well with IgG and IgA antibody titres in COVID-19 patients (17).

## Clinical Study Protocol EBS-CVH-003

Version 4.0, 21 Apr 2021

As previously mentioned, the incubation period for SARS-CoV-2 is approximately 4-5 days (range: 2-7 days) (18), (19), and most individuals who develop symptoms (~98%) will do so within 11.5 days post-infection (18). COVID-19 has various clinical manifestations, including the most commonly reported symptoms of fever, dry cough and dyspnea (shortness of breath); other reported symptoms include fatigue, myalgia, nausea/vomiting or diarrhea, headache, weakness, rhinorrhea, anosmia, ageusia, hypoxia, pneumonia (20), (21), (22). However, current clinical experience with COVID-19 patients indicates hematologic, cardiovascular, renal, gastrointestinal and hepatobiliary, endocrinologic, neurologic, ophthalmologic, and dermatologic symptoms, which may reflect extrapulmonary dissemination and replication of SARS-CoV-2 (23).

Most COVID-19 patients present with mild disease (81%); however, 14% of patients develop severe COVID-19 [characterized by hospitalization (median time from symptom onset to hospitalization is 7 days; range: 3-9 days), (24), worsening of dyspnea and hypoxia, severe pneumonia with >50% lung involvement on imaging], while 5% of patients progress to critical COVID-19 [manifested as respiratory failure/acute respiratory distress syndrome (ARDS), septic shock and/or multiorgan system dysfunction, which can result in death] (19), (22), (25), (26).

Mild COVID-19 resolves 5–7 days (and up to 14 days) after symptom onset without requirement for special medical interventions. Some infected individuals are asymptomatic after SARS-CoV-2 infection but are capable of transmitting the virus (27), (28). Approximately 25% of infected patients have underlying health conditions; however, 60-90% of hospitalized COVID-19 patients have significant comorbidities, including hypertension, obesity, diabetes, cardiovascular disease, chronic pulmonary disease, chronic kidney disease, malignancy and chronic liver disease (24), (29), (30). Abnormal laboratory values observed in hospitalized patients include lymphopenia (83%), elevated inflammatory markers (e.g., C-reactive protein, ferritin, tumor necrosis factor- $\alpha$  (TNF- $\alpha$ ), interleukins (IL-1, IL-6)] indicative of cytokine storm, and abnormal coagulation parameters (e.g., prolonged prothrombin time, thrombocytopenia, elevated D-dimer (46% of patients), low fibrinogen) (31), (32), (33). Complications due to COVID-19 other than lung/pulmonary abnormalities include impaired function of the heart, brain, liver, kidney and coagulation system (23).

Mortality in hospitalized COVID-19 patients ranges from 15% to 20%; however, up to 40% mortality has been observed among patients requiring intensive care unit (ICU) admission (29). In addition, hospital mortality ranges from <5% among patients <40 years to 35% for patients aged 70-79 years and >60% for patients aged 80-89 years (24).

Supportive care, including supplemental oxygen and mechanical ventilation, is the main treatment for severe/critical COVID-19 patients. However, recent clinical studies indicate that dexamethasone decreases mortality (subgroup analysis suggests benefit is limited to patients who require supplemental oxygen and who have symptoms for >7 days) and remdesivir improves time to recovery (subgroup analysis suggests benefit is limited to patients not receiving mechanical ventilation); both are currently recommended for treatment of COVID-19 patients (34), (35). Other classes of drugs are being assessed in clinical studies for treatment of COVID-19 (to either resolve ongoing viremia and/or to manage various COVID-19 manifestations), including antivirals (e.g., umifenovir), antibody-based therapies (e.g., COVID-19 convalescent

plasma), anti-inflammatory agents (e.g., statins), immunomodulatory therapies (e.g., tocilizumab, sarilumab, anakinra, ruxolitinib), anticoagulants [e.g., heparin; albeit, thromboprophylaxis with heparin is currently recommended for hospitalized COVID-19 patients (35)] and anti-fibrotics (e.g., tyrosine kinase inhibitors). Despite the enormous current efforts into clinical investigations of either repurposed drug therapies or development of new products, there are no approved therapeutic interventions to prevent SARS-CoV-2 infection or to treat COVID-19. Therefore, there still exists an unmet medical need for interventions that would resolve SARS-CoV-2 infection and improve clinical outcomes in COVID-19 patients.

## 1.2 Study Drug

### 1.2.1 Anti-SARS-CoV-2 Immunoglobulin Intravenous (Human) – COVID-HIGIV

COVID-HIGIV is a hyperimmune product that consists of purified immunoglobulin (IgG) fraction of human plasma containing antibodies (including neutralizing antibodies) to SARS-CoV-2. COVID-HIGIV is prepared from pooled plasma collected at US Food and Drug Administration (FDA)-licensed and/or registered plasma and/or blood collection centers from healthy, adult donors who have elevated levels of SARS-CoV-2 antibodies.

The final product is a liquid that contains 85–115 mg/mL protein (target 100 mg/mL) of which at least 90% is purified human IgG, stabilized with 250 mM proline and 0.03% polysorbate 80 (PS80), at target pH 5.8. During the viral inactivation step of the manufacturing process, tri-n-butyl phosphate (TnBP) and Triton-X-100 (TX-100) are used and may be presented in trace amounts in the final product [ $\leq$ 1 parts per million (ppm) for TnBP and  $\leq$ 5 ppm for TX-100].

The potency of the final product is determined by a validated immunoassay that measures concentration of binding SARS-CoV-2 antibodies (

) in relation to a standard; the final drug product is also characterized by a wild-type SARS-CoV-2 neutralization assay (refer to the most current version of the Investigator's Brochure).

COVID-HIGIV is provided as a sterile liquid for IV administration only. The product is a clear to slightly opalescent and colorless or pale-yellow liquid essentially free of foreign particles.

The active ingredient of COVID-HIGIV is human immunoglobulin (IgG), which is a normal constituent of the human body and therefore it is not expected to be toxic to humans. At the proposed COVID-HIGIV doses ( $\leq$ 100-400 mg/kg) for this study, exposure levels of excipients (proline, PS80) and residuals (TnBP, TX-100) are well below maximum tolerated doses in animals; hence, these substances are not expected to pose any clinically significant health risks to study subjects (refer to the most current version of the Investigator's Brochure for more details).

Emergent BioSolutions is developing COVID-HIGIV for post-exposure prophylaxis following SARS-CoV-2 exposure and for treatment of COVID-19.

### 1.2.2 COVID-HIGIV as a Therapeutic Intervention for SARS-CoV-2/COVID-19

COVID-HIGIV (code name: NP-028) is intended as a passive immunization therapy (i.e., passive transfer of antibodies) that would provide suitable levels of SARS-CoV-2 antibodies for binding and neutralization of SARS-CoV-2 preventing viral cellular entry and potentially augmenting the immune response.

Although no animal studies have been done to date with COVID-HIGIV, passive transfer of anti-SARS-CoV-2 antibodies with neutralizing activity [e.g., monoclonal antibodies (mAbs) isolated from recovered COVID-19 patients] has been shown to be effective at modulating SARS-CoV-2 infection and reducing viral load (including in the lung tissue) and disease burden in animals after exposure to SARS-CoV-2 (36), (37), (38). In addition, clinical data on passive transfer of SARS-CoV-2 antibodies via transfusion of convalescent plasma collected from individuals who recovered from COVID-19 (i.e., CCP; which contains binding and neutralizing IgA, IgM and IgG antibodies against SARS-CoV-2) to COVID-19 patients suggest that there are no elevated safety risks due to CCP transfusion and that there may be a potential clinical benefit in patients with severe COVID-19 (39), (40), (41), (42), (43).

The overall safety profile of COVID-HIGIV is anticipated to be comparable to other commercially available human hyperimmune IGIV products, including those hyperimmune IGIV products manufactured by Emergent (VARIZIG®, HepaGam B®, ANTHRASIL®, WinRho® SDF, CNJ-016®-VIGIV) (44), (45), (46), (47), (48). The most common types of adverse reactions to hyperimmune IGIV products are non-anaphylactic infusion reactions, such as back or abdominal pain, nausea and vomiting within the first 30 minutes of infusion. Usually there is no dyspnea or other clinically significant changes in vital signs. Fever, headache, chills, rash, fatigue may begin at the end of the IV infusion and continue for several hours. More severe reactions of this type may require treatment with corticosteroids or acetaminophen and persist for several hours after the infusion. These may be treated symptomatically. The incidence of adverse reactions associated with IV administration of immunoglobulin products is reported by the manufacturers to be typically in the range of 1 to 15% (44), (45), (46), (47), (48), (49), (50), (51), (52). Infrequent events associated with IV immunoglobulin treatment have also been reported (mostly in individuals with risk factors for developing these events), such as hypersensitivity reactions, renal failure, aseptic meningitis syndrome (AMS), hemolysis, transfusion-related acute lung injury (TRALI) and thrombotic events (53). Potential risk of antibody-dependent enhancement (ADE) in COVID-19 patients following treatment with antibody-based therapies has not been clinically observed (e.g., in COVID-19 patients after transfusion of convalescent COVID-19 plasma); however, COVID-HIGIV recipients will be closely monitored for disease worsening throughout the study period.

Overall, there is currently proof-of-concept efficacy animal data with SARS-CoV-2 passive antibody transfer (with SARS-CoV-2 mAbs isolated from recovered COVID-19 patients) and some clinical experience with CCP in COVID-19 patients to suggest that an antibody therapeutic such as COVID-HIGIV would elevate SARS-CoV-2 neutralizing antibody levels sufficiently to impact SARS-CoV-2 viral load and to potentially improve clinical outcomes.

### 1.3 Clinical Study Rationale

This study is designed to evaluate safety and PK of three COVID-HIGIV dose levels administered IV as a single dose to healthy adults.

Like other human IGIV products, the hyperimmune products manufactured by Emergent (see Section 1.2.2) have been studied in several healthy adult volunteers and clinical studies with patients; the safety profile of these hyperimmune products is consistent with other commercial IGIV/hyperimmune products and the PK profile is typically similar to PK of licensed IGIV/hyperimmune products, with a half-life of approximately 24 to 30 days after IV administration. The proposed doses for this clinical study ( $\leq 100\text{-}400 \text{ mg/kg}$ ) are within the dose levels tested in clinical studies of other licensed IGIV/hyperimmune products and are expected to display similar safety and PK profile to those products.

Results from this clinical study will provide safety information on the intravenously administered COVID-HIGIV, as well as PK parameters such as peak COVID-HIGIV plasma levels, trough titers of SARS-CoV-2 antibodies and COVID-HIGIV half-life in healthy adults; the safety data and PK parameters from this study (along with data available from other ongoing or planned clinical studies with COVID-HIGIV) will be used for dose optimization/dose selection for the proposed COVID-HIGIV indications (treatment of COVID-19; post-exposure prophylaxis of COVID-19).

## 2 STUDY HYPOTHESIS, OBJECTIVES AND ENDPOINTS

### 2.1 Study Hypothesis

No statistically-powered hypothesis is tested in this Phase 1 study.

### 2.2 Study Objectives

#### 2.2.1 Primary Objectives

The following primary objectives will be evaluated:

- To evaluate PK of three dose levels of COVID-HIGIV administered IV as a single dose to healthy adults.
- To evaluate safety of three dose levels of COVID-HIGIV administered as a single dose to healthy adults.

### 2.3 Study Endpoints

#### 2.3.1 Primary Endpoints

The following primary safety endpoints will be evaluated:

- AEs within 72 hours post-dosing.
- AEs leading to discontinuation or temporary suspension of infusion.
- AEs and SAEs in healthy adults up to 84 days post- administration of a single COVID-HIGIV dose.

The following primary PK endpoints (based on PK sample test results of an immunobinding IgG assay and a pseudovirus neutralization assay) will be evaluated in healthy adults:

- Primary PK Endpoints (at each of the three COVID-HIGIV dose levels):
  - $AUC_{0\text{-last}}$ : area under the concentration-time curve from time 0 to the last quantifiable concentration after dosing.
  - $AUC_{0\text{-inf}}$ :  $AUC_{0\text{-last}}$  plus the additional area extrapolated to infinity after dosing.
  - $AUC_{0\text{-14d}}$  after dosing.
  - $AUC_{0\text{-28d}}$  after dosing.
  - $C_{\max}$ : maximum observed concentration after dosing.
  - $T_{\max}$ : time at which  $C_{\max}$  occurs after dosing.
  - $C_{\min 28d}$ : observed or estimated concentration at 28 days after dosing.
  - $\lambda_z$ : terminal elimination rate constant after dosing.
  - $T_{1/2}$ : apparent terminal elimination half-life after dosing.

- CL: systemic clearance after dosing.
- $V_Z$ : volume of distribution after dosing.

**Secondary PK Endpoints:** following body weight normalized PK parameters will be estimated as PK parameter divided by subject body weight (kg) at baseline.

- CmaxBWN: Body weight normalized Cmax
- Cmin28dBWN: Body weight normalized Cmin28d
- $AUC_{0-14d}BWN$ : Body weight normalized  $AUC_{0-14d}$
- $AUC_{0-28d}BWN$ : Body weight normalized  $AUC_{0-28d}$
- $AUC_{0-last}BWN$ : Body weight normalized  $AUC_{0-last}$
- $AUC_{0-inf}BWN$ : Body weight normalized  $AUC_{0-inf}$

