Record date of the infusion, start/stop times and the total volume infused. For further details, refer to the Pharmacy Manual.

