### **5.1.6 Administration**

Ensure the recipient is adequately hydrated prior to initiation of IV infusion.

Administer COVID-HIGIV by IV infusion through a dedicated IV line using a constant infusion pump (e.g., IVAC® pump or equivalent).

Administer COVID-HIGIV within 24 hours of preparation into an IV infusion bag.

Set the starting infusion rate at 1.0 mL/min for the first 30 minutes. If the infusion is well tolerated, double the infusion rate to 2.0 mL/min for the next 30 minutes, and if tolerated, double the rate to 4.0 mL/min (maximum rate) which should be used for the remainder of the infusion.

For example, at the recommended infusion rates above (with no interruptions or reduction in the infusion rates), dose volume of 400 mL should be infused within 2.5 hours.

Monitor subjects closely during infusion and within 24 hours after completion of COVID-HIGIV infusion.

If AEs occur during the IV infusion, such as grade 1 (mild) events of flushing, headache, chills, fatigue, nausea, slight changes in pulse rate or blood pressure, slow the rate of infusion or temporarily stop the infusion until symptoms subside (at discretion of the investigator). Once the AEs resolve, resume the infusion at a rate that is comfortable to the subject (e.g., start the infusion at half of the last tolerated infusion rate and increase gradually). If the recipient experiences grade 2 (moderate) or higher AEs such as chest pain, difficulty breathing, vomiting, arthralgia, or severe headache, unresponsive to slowing the infusion rate or stopping of the infusion, do not resume the infusion.

Stop the infusion if serious AEs develop (e.g., anaphylaxis, severe hypersensitivity reactions) and administer appropriate medical management. Do not restart the infusion.

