#### **Adverse Events (AE)/Serious Adverse Events (SAE):**

AE will be coded to system organ class (SOC) and preferred term using the Medical Dictionary for Regulatory Activities (MedDRA), using the most current version at the time of coding. AEs will be defined as events beginning after study treatment administration that were not present prior to study treatment administration or those that were present prior to study treatment administration and subsequently worsened in severity.

- AE within 72 hours post-dosing will be summarized by SOC and preferred term.

- AEs and SAEs within 84 days post-dosing will be summarized in the same manner as described above in the first bullet.
- Discontinuation or temporary suspension of infusion will be summarized by treatment group.

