## 8.3 Treatment Compliance

Subjects with incomplete study treatment (i.e., partial infusion) or infusion interruption will be summarized by reason for incompletion and by analysis group for Safety set.

Study drug administration data, such as infusion volume (saline for placebo arm, COVID-HIGIV for other arms), and overall infusion duration will be summarized by analysis group as well.

[COVID-HIGIV]  
[EBS-CVH-003]

A subject listing of study drug administration will be provided including infusion start/end date and time, pharmacist prepared, and subject received infusion volume, infusion duration, and if any infusion interruption the reason(s).

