### **9.3.3 TEAEs Leading to Study Treatment Discontinuation and/or Study Withdrawal**

AEs leading to discontinuation or infusion interruption will be summarized by study arm and listed by subject.

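### The primary endpoint for AEs that stop or suspend the infusion leaves out AEs managed by slowing it or holding the rate, a choice that Protocol 5.1.6 largely leaves to the investigator

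*Protocol*

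**What the plan says.** Protocol 2.3.1 lists "AEs leading to discontinuation or temporary suspension of infusion" as a primary safety endpoint. Protocol 9.3.1 and SAP 3.2 use the same definition. It stands beside two others: AEs within 72 hours of dosing, and AEs and SAEs to 84 days.

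Protocol 5.1.6 governs the infusion. The rate starts at 1.0 mL/min for 30 minutes, goes to 2.0 mL/min for 30 minutes and then to 4.0 mL/min, with each doubling conditional on tolerance. For AEs such as the listed grade 1 examples, staff are to "slow the rate of infusion or temporarily stop the infusion until symptoms subside (at discretion of the investigator"). For AEs of grade 2 or higher, the bar on restarting applies to those "unresponsive to slowing the infusion rate or stopping of the infusion, do not resume the infusion". Only for serious AEs is stopping mandatory: "Stop the infusion if serious AEs develop".

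The planned analyses follow the endpoint wording:

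- Protocol 9.6.2: "Discontinuation or temporary suspension of infusion will be summarized by treatment group".
- SAP 9.3.3: "AEs leading to discontinuation or infusion interruption will be summarized by study arm and listed by subject".
- SAP 8.3: "Subjects with incomplete study treatment (i.e., partial infusion) or infusion interruption will be summarized by reason for incompletion".

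For data capture, Protocol 5.1.5 says "Record date of the infusion, start/stop times and the total volume infused" and refers to the Pharmacy Manual for more. SAP 8.3 adds infusion duration and the reasons for any interruption. Neither document names a record or a table of rate changes.

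**The concern.** The endpoint is defined by what the investigator did, and 5.1.6 offers two answers to the same mild reaction without saying when to use which. A pause is an event; a rate reduction is not. Holding the rate instead of doubling it is not an event either, nor is a non-serious grade 2 or higher AE that settles with slowing.

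This matters because failure to tolerate the scheduled rate could be related to dose. SAP 2.3.3 has every bag at 400 mL, and 5.1.6 sets one schedule in mL/min. At equal body weight, the 400 mg/kg arm therefore receives 400/100 = 4 times as much product per minute as the 100 mg/kg arm. Protocol 1.3 says that the safety data will feed dose selection. The study tests no hypothesis, so the counts by arm are themselves the result.

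**Working it through.** There is no sample size, power or alpha figure to reproduce for this point: Protocol 2.1 and 9.1 say the study is descriptive. The check is a trace of the definition, then its numerical weight, then whether other planned data could stand in.

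**1. How each management action is scored**

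| Response to an AE during infusion | Room for it in 5.1.6 | Stop/suspend endpoint | 72-hour and 84-day AE endpoints |
|---|---|---|---|
| Rate increase withheld | Yes; doubling depends on tolerance | Not counted | Counted |
| Rate reduced, AE settles | Yes; investigator's choice for mild AEs, not excluded for non-serious grade 2 or higher | Not counted | Counted |
| Paused, then resumed | Yes; investigator's choice for mild AEs | Counted | Counted |
| Stopped for good | Yes; unresponsive grade 2 or higher, and serious AEs | Counted | Counted |

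The last column holds because SAP 9.2.1 opens the 72-hour window at the start of infusion and takes all AEs whatever the action.

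**2. Weight of one choice.** The arms are 8, 8, 8 and 4 (Protocol 3.3). One reaction slowed instead of paused moves an active arm by 1/8 = 12.5 percentage points and the placebo arm by 1/4 = 25 points. Three identical mild reactions in an active arm can score anywhere from 0/8 (exact 95% CI 0 to 36.9%) to 3/8 (8.5 to 75.5%).

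**3. Illustration.** Let r be the share of subjects with a reaction that prompts some change to the infusion, and q the share of those reactions handled by a pause or stop. Neither is given in the documents. Protocol 1.2.2 quotes 1 to 15% for all adverse reactions to IV immunoglobulins, some of which begin only as the infusion ends, so 15% is used only as a generous upper value. With n = 8,

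P(at least one endpoint event) = 1 − (1 − rq)^8.

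| r | q = 0 | q = 0.25 | q = 0.5 | q = 0.75 | q = 1 |
|---|---|---|---|---|---|
| 5% | 0% | 9.6% | 18.3% | 26.3% | 33.7% |
| 15% | 0% | 26.3% | 46.4% | 61.5% | 72.8% |

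For example, at r = 15% and q = 0.5, 1 − 0.925^8 = 46.4%. If every infusion modification were counted, the result would be the q = 1 column whichever action was chosen.

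If q is the same in all arms, each arm's expected rate is rq. Differences between arms then shrink by the factor q, but their direction does not change. With assumed r of 5% and 15%, the expected difference is 10 points at q = 1 and 5 points at q = 0.5.

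**4. Can infusion duration stand in?** On the 5.1.6 schedule, the first hour delivers 30 × 1 + 30 × 2 = 90 mL. The remaining 310 mL takes 310/4 = 77.5 min. The total is 137.5 min, or 2.29 h, which agrees with the protocol's statement that 400 mL should be infused within 2.5 hours. Running at 2 instead of 4 mL/min for 20 minutes leaves 20 × 2 = 40 mL to make up, which takes 40/4 = 10 min. A 10-minute pause resumed at full rate also adds 10 min. The duration is 147.5 min in both cases, yet only the pause is an event. A summary of duration by arm cannot tell the two apart.

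**The case against.** The strongest reply is that little is lost. The reaction enters two other primary endpoints, and SAP 9.2.1 also tabulates AEs by maximum severity and by relatedness. The endpoint is openly about stopping and suspending; any endpoint of this type reflects the clinician's response, and adding rate changes makes a broader one. No stated decision uses the count: the pause rule in Protocol 8.11 rests on SAEs and on repeated grade 2 or 3 AEs.

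Most of this stands, and it sets the weight of the point. It does not close the gap. The 72-hour tables are by SOC and preferred term, so they do not separate a headache that forced a rate reduction from a later one that needed nothing.

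Three stronger inferences are tempting, and the documents do not support them:

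- **The comparison between doses is biased.** A reader might infer that one dose was slowed and another paused by preference. There is one site, investigators are blinded, bags are covered and of equal volume (Protocol 3.5), and placebo follows the same rate steps (Protocol 5.2). Nothing points to a different habit in different arms.
- **A dose managed by slowing would look free of reactions.** It would show zero on this row only.
- **Rate changes are not recorded.** The blank CRF and the Pharmacy Manual are cited but not included, so this is unknown. Even without such a record, the subject listings in SAP 8.3 (start, end, volume, duration, interruptions) can be set against the AE listing in SAP 9.2. A full 400 mL infusion that ran well past 137.5 min with no interruption, and with an AE starting during it, points to a slowed or held rate. With 28 subjects that is feasible, though indirect and not planned as a table.

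**Conclusion.** The point holds for this endpoint alone. Protocol 2.3.1 and 9.3.1 and SAP 3.2 and 9.3.3 do not count AEs managed by slowing or by withholding a rate increase, while 5.1.6 leaves that choice to the investigator for mild AEs and does not require stopping for non-serious grade 2 or higher AEs that respond to slowing. Serious AEs are unaffected, because stopping is mandatory.

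The consequence is under-counting and noise, at 12.5 percentage points per choice in an active arm. The probabilities in the illustration rest on assumed values of r and q and show only how far the result can depend on the action chosen. The safety objective as a whole is not undermined. This is an inexpensive improvement to one row of the primary safety results.

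**What to change.** If the eCRF does not already do so, record AE-driven rate reduction or withheld rate increase, with its time, as an action taken for the AE.

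In SAP 9.3.3 and Protocol 9.6.2, tabulate by arm the AEs leading to any infusion modification: rate reduced or increase withheld, interrupted, or discontinued. Keep the present stop/suspend count as a sub-row, so that nothing prespecified is lost.

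If dosing is complete and rate actions were not recorded, add a table by arm of AEs with onset during the infusion, shown alongside infusion duration.

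The cost is at most one eCRF option and one table row, or one extra table. The reported count of infusion-related events may look slightly less favourable. Infusion management under 5.1.6 is unchanged.
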